5.8 Handling of Missing and Incomplete Data

In case of missing data for any variable, the information on the number of patients with missing data will be displayed in the appropriate output(s). For categorical variables, the percentages will be calculated based on all available data (missing and non-missing). The subjects with missing information will be included in the calculations.

Regarding the analysis of the primary outcome, it is not expected to have missing information regarding the start date of afatinib (Gi(l)otrif[®]) treatment. For patients still on treatment, time on treatment will be censored at the date of completion of data collection. For patients lost to follow-up and still on treatment, time on treatment will be censored at the date the patient was last known to be alive.

The possibility of having missing date for ECOG PS is foreseen and no imputation rules will be applied.

5.8.1 Partial Dates

The following dates will be collected completed (no partial dates are accepted) in the CRF: 'date of visit' (date of the first day of data entry), 'date of informed consent', 'date of date entry completion' and 'date of consent withdrawal'. For the other dates, the following rules will be applied.

In case the day is missing and the month and year are given:

- the 15th of the month for:
 - Start date of initial dose (afatinib (Gi(l)otrif[®]))

Statistical Analysis Plan Template For Observational Studies

Boehringer Ingelheim
Protocol c14668275-02

Statistical Analysis Plan

- the end day of last dose of afatinib (Gi(l)otrif[®]) if the month and year are same otherwise the 15th of the month for:
 - Start date of initial dose (osimertinib)
- the end day of the previous dose if the month and year are the same otherwise the 15th of the month for:
 - Start date of modified dose (afatinib (Gi(l)otrif[®]))
 - Start date of modified dose (osimertinib)
- the start day of the next dose if the month and year are the same otherwise the 15th of the month for:
 - End date of initial dose (afatinib (Gi(l)otrif[®]))
 - End date of initial dose (osimertinib)
 - End date of modified dose (afatinib (Gi(l)otrif[®]))
 - End date of modified dose (osimertinib)
- The day of last dose of osimertinib if the month and year are the same otherwise the 15th of the month for:
 - Date of death
 - Date patient was last known to be alive

If day and month are missing and year is given:

- The day and month of last dose of osimertinib if the year is the same otherwise the 1st of January for:
 - Date of death
 - Date patient was last known to be alive

In case the end date of one dose and start date of the next dose are partially given and they are the same (e.g. September 2017), is assumed the 15th day of the month for the former and the 16th day for the latter.

The same is assumed for the end date of afatinib (Gi(l)otrif[®]) and start date of osimertinib.

Patients with a substantial amount of missing and/or partial dates may be replaced according to section 5.1.

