3.5.2 Primary Outcome

Time on treatment with afatinib (Gi(l)otrif[®]) followed by osimertinib.

This will be assessed as the time from start of afatinib (Gi(l)otrif[®]) as first-line treatment until the end of the second-line treatment (last dose of osimertinib) or death date by any cause.

Statistical Analysis Plan Template For Observational Studies

Boehringer Ingelheim
Protocol c14668275-02

Statistical Analysis Plan

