5.3 Study Patients

A clear accounting of the disposition of all patients who enter the study will be provided.

- A summary of the number of patients checked for entry into the study and the number and percentage of patients not included by major reason – not meeting an Inclusion criterion or meeting an Exclusion criterion – and overall T14.1.1.1
 - A summary of the number and percentage of patients included - per center, per country and region T14.1.1.2
 - A summary of the number and percentage of dead patients and patients not completing the study, as well as the follow-up time in the study, calculated as below. T14.1.1.3
- Follow – up Time (months) = (Data entry completion date – Start date of afatinib)/30.4375*

Two by-patient listings will be provided:

- For all patients checked for entry, one listing will be presented with the date of first day of data entry, the Inclusion and Exclusion criteria and date of informed consent (if applicable) L16.2.1.1
- For all patients included in the study, one listing with the status at data entry completion will be presented. This listing will include at least the subject status and data of death / lost to follow-up (if applicable) L16.2.1.2

Statistical Analysis Plan Template For Observational Studies

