5.6 Statistical methods

5.6.1 Analysis of the Primary Outcome

The primary outcome is time on treatment, which is defined as time in months from the start date of afatinib (Gi(l)otrif[®]) treatment – ‘start date of initial dose’ for First Line Treatment – to the end date of osimertinib treatment – maximum between ‘end date of initial dose’ and the last ‘end date of dose modification’ for Second Line Treatment – or death date due to any cause – ‘date of death’.

$$\text{Time on treatment (months)} = \text{time on treatment (days)} / 30.4375$$

Time on treatment will be analysed using Kaplan-Meier method, and the median along with two-sided 90% confidence interval will be displayed using the Greenwood’s formula for estimation of standard errors.

The primary outcome will be analysed in SAS using the LIFETEST procedure as follows:

```
proc lifetest data=mydata alphaqt=0.1  
  plots=survival(atrisk failure);  
  time t*event(0);  
run;
```

where **alphaqt** specifies the 90% confidence interval; the **t** variable is the time in months from the start date of afatinib (Gi(l)otrif[®]) treatment to the end date of osimertinib treatment or death; and the **event** variable specifies the subjects for which the whole information is present (=1) or were censored (=0). T14.2.3.1

The time on treatment (afatinib, osimertinib and total) will be summarized through descriptive statistics and survival plots will be provided. F14.2.3.5

Statistical Analysis Plan Template For Observational Studies

Boehringer Ingelheim
Protocol c14668275-02

Statistical Analysis Plan

Both tables and plots will be repeated for the following subgroups: Ethnicity, Race, EGFR mutation, Gender, Brain metastases at start of Afatinib, Brain metastases at any time, Age group 1, Age group 2, ECOG and Data Source. T14.2.3.2
F14.2.3.6
T14.2.3.8
F14.2.3.10

For the subgroup analyses, the log-rank test results will be provided. These results may be obtained introducing the strata statement in the LIFETEST procedure as follows: T14.2.3.12
F14.2.3.14

```
proc lifetest data=mydata alphaqt=0.1  
  plots=survival(atrisk failure);  
  time t*event(0);  
  strata subgroup;  
run;
```

For the total time on treatment, the information on the number and percentage of censored patients will also be summarized. T14.2.3.3

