This table will be repeated for the following subgroups: Ethnicity, Race, EGFR mutation, Gender, Brain metastases at start of Afatinib, Brain metastases at any time, Age group 1, Age group 2, ECOG and Data Source. T14.2.3.4

Time between end of afatinib and start of osimertinib will be summarized through descriptive statistics. T14.2.3.15

Time between end of osimertinib and death will be analyzed in a similar way as the primary outcome. T14.2.3.16
F14.2.3.17

Swimmer plots displaying time on afatinib treatment, time between end of afatinib and start of osimertinib and time in osimertinib treatment for each patient will be provided. F14.2.3.18

By-patient listings will be provided including at least the time on treatment (afatinib, osimertinib and total), time between end of afatinib and start of osimertinib, time between end of osimertinib and death and information whether the patient was censored or not. L16.2.6.6
L16.2.6.7
L16.2.6.8

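### SAP 5.8.1 sets a day-missing final osimertinib stop to the 15th without checking it against a known death date or the start of that dose (minor)

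*SAP*

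**What the plan says.** Section 5.8.1 lists the end dates of initial and modified doses, for afatinib and osimertinib alike, under one rule for a missing day: "the start day of the next dose if the month and year are the same otherwise the 15th of the month for" these dates.

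The same section orders dates in two other situations. A death or last-known-alive date with a missing day is tied to treatment: "The day of last dose of osimertinib if the month and year are the same otherwise the 15th of the month for" both. Two adjoining partial dose dates are separated as the 15th and 16th: "In case the end date of one dose and start date of the next dose are partially given and they are the same". That device is extended to the end of afatinib and the start of osimertinib.

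Two analyses depend on the osimertinib end date:

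- The primary outcome (section 3.5.2) runs "until the end of the second-line treatment (last dose of osimertinib) or death date by any cause". Section 5.6.1 takes the osimertinib end as the "maximum between ‘end date of initial dose’ and the last ‘end date of dose modification’ for Second Line Treatment".
- Section 5.6.1 adds: "Time between end of osimertinib and death will be analyzed in a similar way as the primary outcome". That means Kaplan-Meier, reported in T14.2.3.16 and F14.2.3.17.

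**The concern.** The order of stop and death is protected in one direction only. A partial death date is adjusted to a known last dose, but a partial last dose is not adjusted to a known death date. Nor is the imputed end of a dose compared with that dose's own start.

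Nothing later in the SAP repairs this. The automatic checks in section 5.1 act on what is entered. A stop entered as May 2017 and a death on 4 May 2017 are consistent as entered; they conflict only after imputation. Patient replacement is discretionary and aimed at substantial missing data, not at one missing day.

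The situation is foreseeable. The data come retrospectively from medical records, partial dose dates are provided for, and section 3 asks that deceased patients be enrolled where possible. A negative time is not valid Kaplan-Meier input, so the record is either lost or repaired by an unplanned rule. Either way, the affected patients are those who died soonest after stopping.

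**Working it through.** The SAP gives no figure on this point to reproduce, so the rule was applied day by day. Inputs: the imputation rule (5.8.1), 30.4375 days per month (5.3 and 5.6.1), and the assumed median of 24 months (5.9).

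**1. Known death in the stop month.** Imputed stop = day 15; death = day d. Stop minus death = 15 − d, which is positive for d = 1 to 14.
- Range: 1 to 14 days, mean 7.5 days.
- Maximum: 14 / 30.4375 = 0.46 months.

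**2. How often, within that subset.** This needs an assumption about the true days.
- Day of death uniform over the month: 14 / 30.4375 = 46% (14/31 = 45% to 14/28 = 50% by month length). This would fit, for example, patients who stopped on the day they died.
- All pairs with stop on or before death equally likely, 30-day month: 30 × 31 / 2 = 465 pairs. Pairs with death on day 14 or earlier: 14 × 15 / 2 = 105. 105 / 465 = 23%.

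These are two illustrations, not bounds. Both are conditional on a missing stop day, a complete death date, and both dates in the same month and year.

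**3. Last dose started in the stop month.** Start on day s; imputed end minus start = 15 − s, which is negative for s = 16 or later. The record ends before it begins by up to 13, 15 or 16 days in months of 28, 30 or 31 days. Maximum: 16 / 30.4375 = 0.53 months.

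**4. Worked example (assumed dates).** Afatinib start 1 June 2015; osimertinib stop recorded as May 2017, imputed as 15 May 2017.
- Afatinib start to imputed stop: 714 / 30.4375 = 23.46 months.
- Known death on 4 May 2017: 703 / 30.4375 = 23.10 months. End of osimertinib to death = −11 / 30.4375 = −0.36 months. Capping the stop at death makes it 0.
- Last dose started on 24 May 2017 instead: the record ends 9 days before it begins. A floor at the start gives at least 723 / 30.4375 = 23.75 months.

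**5. The maximum rule in 5.6.1, applied to the 24 May case.**
- Initial dose ended on 23 May: the maximum picks 23 May, so osimertinib time is nearly right although the last record is still impossible.
- Initial dose end also day-missing in May: it takes the next dose's start, 24 May, and the maximum picks that.
- Initial dose ended before 15 May or in an earlier month: the maximum is 15 May and osimertinib time is too short.
- Preceding dose itself a modification: the result depends on whether the last modification end means the last record or the latest date.

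**6. Afatinib.** Suppose afatinib ended in May 2017 (day missing) and osimertinib started on 10 May 2017. If the next dose includes osimertinib, the end becomes 10 May. If not, it becomes 15 May and the gap in T14.2.3.15 is −5 days. The 15th/16th device does not apply, because only one of the two dates is partial.

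**The case against.** The gap in 5.8.1 is hard to dispute; its consequences are easy to overstate. Five points on the other side have force.

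- **Primary time and death.** A reader might infer that time on treatment runs past death. In a time-to-event definition, ending at stop or death ordinarily means whichever comes first. A later-of reading would carry every patient who died after stopping through to death, which clashes with the separate analysis of osimertinib end to death. Under the natural reading, an imputed stop after death is cut at death and the primary time is unaffected. This stands; the missing words are a clarification.
- **Before-start case.** The maximum rule often rescues the primary time, as step 5 shows. This stands, though not for every dose history, and the dose record itself remains wrong.
- **Plots and durations.** A reader might expect negative bars in the swimmer plots. The plots show whole phases, so a negative osimertinib bar needs the entire phase to begin after the 15th and stop in the same month. No summary of single-dose durations is planned. This stands.
- **Scope.** Not every patient who dies in the stop month is affected; all the conditions in steps 1 and 2 must hold together. This stands.
- **Importance.** Time from osimertinib end to death is not among the outcomes in sections 3.5.2 and 3.5.3. This stands and bears on severity.

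None of these removes the negative times from T14.2.3.16 and F14.2.3.17. Those follow from a stated rule, not from detail left to programming.

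**Conclusion.** The point holds as a minor one. Followed as written, the rule can place the end of osimertinib after a known death, or before the start of the last dose. The clearest damage is to the Kaplan-Meier analysis of osimertinib end to death. If negative times are dropped, that analysis loses its shortest survivors and the estimate would tend upward. The size cannot be given, because the SAP does not state how many stop dates lack a day.

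For the primary outcome the effect is probably small. The largest shift per affected patient is about half a month, against an assumed median of 24 months (0.53 / 24 = 2.2%), and only some patients could be affected. There is none from the death case if the outcome ends at whichever event comes first. A reader might conclude that the primary median is unreliable; the documents do not support that.

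**What to change.** In section 5.8.1:
- Keep the 15th for a day-missing osimertinib end date, but no earlier than the start of that dose and no later than a known date of death, last-known-alive date or data entry completion. The last two caps follow the same logic: an imputed stop should not fall after the last date on which the patient or the record was observed.
- Apply the same floor, the start of the dose, to afatinib end dates.
- State that the next dose after the last afatinib dose includes a known osimertinib start.

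In section 5.6.1, state that the primary time ends at the earlier of the last osimertinib dose and death.

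The cost is a few lines of SAP wording and programming. No new data are needed.

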5.9 Determination of Sample Size

It is assumed that the median time on treatment from start of the first-line treatment until the end of the second-line treatment or death date by any cause is 24 months (based on: 13.6 months median PFS with afatinib (Gi(l)otrif[®]) in LUX-Lung 3, 13.7 months time to treatment failure with afatinib (Gi(l)otrif[®]) in LUX-Lung 7 plus 10.1 months median PFS of osimertinib in AURA-3, 13.2 months in the AURA study phase 2 extension component (P17-01960, P17-03000). Based on the assumption that time on treatment follows an exponential distribution, a sample size of 171 patients are expected to ensure at 80% chance to observe a width of the 90% confidence interval of median time on treatment smaller or equal to 10 months, which is considered as a reasonable estimation precision. Assuming 10% of censored observations a total of 190 patients are included in the study.

Statistical Analysis Plan Template For Observational Studies

Boehringer Ingelheim
Protocol c14668275-02

Statistical Analysis Plan

